5.2. Exclusion Criteria

Participants are excluded from the study if any of the following criteria apply:

- [12] Have previously completed or withdrawn from this study, participated in any other study with ixekizumab, or have participated in any study investigating other IL-17 antagonists.
- [13] Have a history of drug-induced PsO.
- [14] Concurrent or recent use of any biologic agent within the following washout periods: etanercept <28 days; infliximab, adalimumab, or alefacept <60 days; golimumab <90 days; ustekinumab <8 months; rituximab or efalizumab <12 months; or any other biologic agent <5 half-lives prior to baseline (Week 0 Visit 2).
- [15] Cannot avoid excessive sun exposure or use of tanning booths for at least 4 weeks prior to baseline (Week 0; Visit 2) and during the study.
- [16] Have a known allergy or hypersensitivity to any biologic therapy that would pose an unacceptable risk to the patient if participating in this study.
- [17] Have ever received natalizumab or other agents that target alpha-4-integrin.
- [18] Had a live vaccination within 12 weeks prior to baseline (Week 0; Visit 2), or intend to have a live vaccination during the course of the study, or within 12 months of completing treatment in this study, or have participated in a vaccine clinical study within 12 weeks prior to baseline (investigators should review the vaccination status of their patients and follow the local guidelines for adult vaccination with non-live vaccines intended to prevent infectious disease prior to therapy).

Note: Killed/Inactive or subunit vaccines are expected to be safe; however, their efficacy with concomitant ixekizumab treatment is unknown.

- [19] Had a vaccination with Bacillus Calmette-Guérin (BCG) within 12 months prior to baseline (Week 0; Visit 2), or intend to have this vaccination with BCG during the course of the study, or within 12 months of completing treatment in this study.
- [20] Had any major surgery within 8 weeks prior to baseline (Week 0; Visit 2), or will require such during the study that, in the opinion of the investigator in consultation with Lilly or its designee, would pose an unacceptable risk to the patient.
- [21] Have current or a history of lymphoproliferative disease; or signs or symptoms of lymphoproliferative disease; or have active or history of malignant disease.
- [22] Have diagnosis or history of malignant disease within the 5 years prior to baseline (Week 0, Visit 2).

Note: Patients with successfully treated basal-cell carcinoma (no more than 3), squamous-cell carcinoma of the skin, or cervical carcinoma in situ, with no evidence of recurrence within the 5 years prior to baseline (Week 0; Visit 2) may participate in the study.
- [23] Presence of significant uncontrolled cerebrocardiovascular (e.g., MI, unstable angina, unstable arterial hypertension, moderate-to-severe [New York Heart Association (NYHA) class III/IV] heart failure, or cerebrovascular accident [CVA]), respiratory, hepatic, renal, gastrointestinal, endocrine, hematologic, neurologic or neuropsychiatric disorders, or abnormal laboratory values at screening that, in the opinion of the investigator, pose an unacceptable risk to the patient if participating in the study or of interfering with the interpretation of data.
- [24] Have had fluid overload, MI or new onset ischemic heart disease (e.g., unstable angina), uncompensated heart failure, or in the opinion of the investigator other serious cardiac disease within 12 weeks prior to baseline (Week 0; Visit 2).
- [25] Have a current or recent acute, active infection (for at least 30 days before screening (Visit 1), participants must have no symptoms or signs of confirmed or suspected infection and must have completed any appropriate anti-infective treatment).

Note: Participants who have an upper respiratory infection, a vaginal candida infection, or an oral candida infection and who are being treated only symptomatically and not requiring systemic anti-infectives may be considered for enrollment if other study eligibility criteria are met. Enrollment of participants with other uncomplicated local infections should be discussed with the Sponsor's designated medical monitor.

[26] Have had any of the following types of infection within 3 months prior to the screening visit (Visit 1):

- Serious (requiring hospitalization, or intravenous or equivalent oral antibiotic treatment, or both).
- Opportunistic (as defined in Winthrop et al. 2015).

Note: Herpes zoster is considered active and ongoing until all vesicles are dry and crusted over.

- Chronic (duration of symptoms, signs, and/or treatment of 6 weeks or longer).
- Recurring (including, but not limited to, herpes simplex, herpes zoster, recurring cellulitis, chronic osteomyelitis).

Note: Participants with only recurrent mild and uncomplicated orolabial herpes, or genital herpes, or both may be discussed with the Sponsor's designated medical monitor and considered for enrollment if other study eligibility criteria are met.

[27] Have active TB (refer to Section 8.2.7 for details on determining full TB exclusion criteria).

[28] Have any other active or recent infection within 4 weeks of baseline (Week 0; Visit 2) that, in the opinion of the investigator, would pose an unacceptable risk to the patient if participating in the study; these patients may be rescreened (1 time) 4 or more weeks after documented resolution of symptoms.

[29] Have a body temperature $\geq 38^{\circ}\text{C}$ (100.5°F) at baseline (Week 0; Visit 2); these patients may be rescreened (1 time) ≥ 4 weeks after documented resolution of elevated temperature.

[30] Have uncontrolled arterial hypertension characterized by a systolic blood pressure (SBP) >160 mm Hg or diastolic blood pressure (DBP) >100 mmHg.

Note: Determined by 2 consecutive elevated readings. If an initial blood pressure (BP) reading exceeds this limit, the BP may be repeated once after the patient has rested sitting for ≥ 10 minutes. If the repeat value is less than the criterion limits, the second value may be accepted.

[31] Are positive for human immunodeficiency virus (HIV) serology (positive for human immunodeficiency virus antibody [HIVAb]).

[32] Have evidence of or test positive for hepatitis B by any of the following criteria:
1) positive for hepatitis B surface antigen (HBsAg+); 2) positive for anti-hepatitis B core antibody (HBcAb+) and negative for anti-hepatitis B surface antibody (HBsAb-); 3) positive for anti-hepatitis B core antibody (HBcAb+) and positive for anti-hepatitis B surface antibody (HBsAb+) with a concentration of HBsAb <200 mIU/mL; or 4) HBcAb+, HBsAb+ (regardless of HBsAb level), and positive for serum hepatitis B virus (HBV) DNA.

Note: Patients who are negative for hepatitis B surface antigen (HBsAg-), HBcAb+, HBsAb+ with a concentration of HBsAb \geq 200 mIU/mL, and negative for serum HBV DNA may participate in the study. Patients who meet these criteria at screening will be identified by the central laboratory and monitored during the study as detailed in Section 8.2.8.1.

[33] Have evidence of or test positive for hepatitis C virus (HCV). A positive test for HCV is defined as: 1) positive for hepatitis C antibody (anti-HCVAAb), and 2) positive via a confirmatory test for HCV (e.g., HCV polymerase chain reaction [PCR]).

[34] Have clinical laboratory test results at screening that are outside the normal reference range for the population and are considered clinically significant, and/or have any of the following specific abnormalities:

- [34a] Neutrophil count <1500 cells/ μ L
- [34b] Lymphocyte count <500 cells/ μ L
- [34c] Platelet count <100,000 cells/ μ L
- [34d] Aspartate aminotransferase (AST) or alanine aminotransferase (ALT) >2.5 times the upper limit of normal (ULN)
- [34e] Total white blood cell (WBC) count <3000 cells/ μ L
- [34f] Hemoglobin <8.5 g/dL (85.0 g/L) for male patients and <8.0 g/dL (80 g/L) for female patients
- [34g] Serum creatinine >2.0 mg/dL

Note: The AST and ALT may be repeated once within a week if the initial response exceeds this limit, and the repeat value may be accepted if it meets this criterion. Other laboratory tests should not be repeated unless there is a technical error or clinical reasons to believe a result may be erroneous.

[35] Have electrocardiogram (ECG) abnormalities that are considered clinically significant and would pose an unacceptable risk to the patient if participating in the study.

[36] Have any other condition that precludes the patient from following and completing the protocol, in the opinion of the investigator.

[37] Have donated blood of >500 mL within the last 4 weeks, or intend to donate blood during the course of the study.

- [38] Are women who are lactating or breastfeeding.
- [39] Are investigator site personnel directly affiliated with this study and/or their immediate families. Immediate family is defined as a spouse, parent, child, or sibling, whether biological or legally adopted.
- [40] Are Lilly employees or its designee or are employees of third-party organizations (TPOs) involved in the study.
- [41] Are currently enrolled in, or discontinued from a clinical trial involving an investigational product or nonapproved use of a drug or device within the last 4 weeks or a period of at least of 5 half-lives of the last administration of the drug, whichever is longer, or concurrently enrolled in any other type of medical research judged not to be scientifically or medically compatible with this study.

PsO Participants

- [42] Have received systemic non-biologic PsO therapy (including, but not limited to, oral psoralens and ultraviolet A [PUVA] light therapy; cyclosporine; corticosteroids; methotrexate [MTX]; oral retinoids; mycophenolate mofetil; thioguanine; hydroxyurea; sirolimus; azathioprine; fumaric acid derivatives; or 1,25 dihydroxy vitamin D3 and analogues) or phototherapy (including either oral and topical PUVA light therapy, ultraviolet B [UVB] or self-treatment with tanning beds or therapeutic sunbathing) within 4 weeks prior to baseline (Week 0; Visit 2); or had topical PsO treatment (including, but not limited to, corticosteroids, anthralin, calcipotriene, topical vitamin D derivatives, retinoids, tazarotene, emollients and other non-prescription topical products containing urea, >3% salicylic acid, or alpha- or beta-hydroxyl acids, and medicated shampoos [e.g., those that contain >3% salicylic acid, corticosteroids, coal tar, or vitamin D3 analogues]) within the previous 2 weeks prior to baseline (Week 0; Visit 2).

Exceptions: class 6 (mild, such as desonide) or class 7 (least potent, such as hydrocortisone) topical steroids will be permitted for use limited to the face, axilla, and/or genitalia.

- [43] Have pustular, erythrodermic, and/or guttate forms of PsO.
- [44] Had a clinically significant flare of PsO during the 12 weeks prior to baseline (Week 0; Visit 2).
- [45] Have allergy to rubber or latex.

PsA Participants

- [46] Have used conventional synthetic disease-modifying antirheumatic drug (csDMARDs) other than MTX, leflunomide, sulfasalazine, or cyclosporine in the 8 weeks prior to baseline (Week 0; Visit 2).

Have discontinued MTX, sulfasalazine, or cyclosporine within 12 weeks prior to baseline (Week 0; Visit 2).

If taking MTX, leflunomide, sulfasalazine, or cyclosporine, must have been treated for at least 12 weeks prior to baseline *and* on a stable dose for at least 8 weeks prior to baseline, as follows: oral or parenteral MTX = 10 to 25 mg/week; leflunomide = 20 mg/day; sulfasalazine = up to 3 g/day; or cyclosporine up to 5 mg/kg/day. The dose of these allowed concomitant medications must remain unchanged during the study periods of the unless changes are required for safety issues. Local standard of care should be followed for concomitant administration of folic acid with MTX.

[47] Are currently receiving treatment with any biologic or small molecule therapy for PsA or PsO, including investigational therapies (such as, but not limited to, a TNFi, IL-1 receptor antagonists, IL-6 inhibitor, anti-IL-12/23p40, T cell or B cell targeted therapies, phosphodiesterase [PDE] 4 inhibitors, or Janus kinase [JAK] inhibitors), or have received denosumab.

[48] Have received treatment with IL-17 or IL12/23 targeted Mab therapy.

[49] Have used disease-modifying antirheumatic drug (DMARDs) other than MTX, leflunomide, sulfasalazine, or hydroxychloroquine (e.g., gold salts, cyclosporine, azathioprine, dapsone, 6-mercaptopurine, mycophenolate mofetil, or any other immunosuppressive agents) in the 8 weeks prior to baseline (Week 0, Visit 2).

Have discontinued MTX or sulfasalazine within the 8 weeks prior to baseline, or hydroxychloroquine within 12 weeks prior to baseline.

If taking MTX, leflunomide, sulfasalazine, or hydroxychloroquine must have been treated for at least 12 weeks prior to baseline and on a stable dose for at least 8 weeks prior to baseline, as follows: oral or parenteral MTX = 10 to 25 mg/week; leflunomide = 20 mg/day; sulfasalazine = up to 3 g/day; or hydroxychloroquine = up to 400 mg/day. The dose of these allowed concomitant medications must remain unchanged until W12 of the study, unless changes are required for safety issues. Local standard of care should be followed for concomitant administration of folic acid with MTX.

[50] Are receiving treatment with more than 1 conventional DMARD (MTX, leflunomide, sulfasalazine, or hydroxychloroquine) at study entry.
Note: Under no circumstances will simultaneous use of MTX and leflunomide be allowed at any time during the study for safety reasons.

[51] Have discontinued leflunomide within 4 weeks prior to baseline or have received leflunomide from 4 to 12 weeks prior to baseline (Week 0, Visit 2) and have not undergone a drug elimination procedure.

[52] Use of oral corticosteroids at average daily doses of >10 mg/day of prednisone or its equivalent, or use of variable doses of any oral corticosteroids, within 4 weeks prior to baseline (Week 0, Visit 2).

- [53] Have received any parenteral glucocorticoid administered by intraarticular, intramuscular, or intravenous (IV) injection within 6 weeks prior to baseline (Week 0, Visit 2), or for whom a parenteral injection of glucocorticosteroids is anticipated until W12 of the study.
- [54] Concomitant use of nonsteroidal anti-inflammatory drug (NSAIDs), including cyclooxygenase-2 (COX-2) inhibitors, unless the patient is on a stable dose for at least 2 weeks prior to baseline (Week 0, Visit 2).
- [55] Use of any opiate analgesic at average daily doses of >30 mg/day of morphine or its equivalent or use of variable doses of any opiate analgesic within 6 weeks prior to baseline (Week 0, Visit 2).
- [56] Have a diagnosis of other inflammatory arthritic syndromes such as rheumatoid arthritis (RA), ankylosing spondylitis, reactive arthritis, or enteropathic arthritis.
- [57] Have active Crohn's disease or active ulcerative colitis.
- [58] Have diagnosis of fibromyalgia.
- [59] Have a chronic pain condition that would confound evaluation of the patient.
- [60] Have evidence of active vasculitis or uveitis.
- [61] Have had surgical treatment of a joint within 8 weeks prior to baseline or will require such up to Week 24.

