6.1. Study Intervention(s) Administered

Table RHCZ.6.1. Treatment Regimens

Treatment Group	Starting Dose W0	Dose W2-W10	Dose ^a W12-W20
Ixekizumab for 
 • PsO participants with no active PsA • PsA participants who meet criteria for moderate-to-severe PsO 	Ixekizumab 80 mg × 2 SC (total of 160 mg)	Ixekizumab 80 mg SC Q2W at W2, 4, 6, 8, and 10	Ixekizumab 80 mg SC Q4W at W12, 16, and 20
Ixekizumab for PsA participants who do not meet criteria for moderate-to-severe PsO	Ixekizumab 80 mg × 2 SC (total of 160 mg)		Ixekizumab 80 mg SC Q4W at W4, 8, 12, 16, and 20

Abbreviations: PsA = psoriatic arthritis; PsO = psoriasis; Q2W = every 2 weeks; Q4W = every 4 weeks; SC = subcutaneous injection; W = week.

^a No dose is given at W24; therefore, W24 is not included in this table.

Note: When the dosing is scheduled at home (for PsO participants with no active PsA and PsA participants who meet criteria for moderate-to-severe PsO: W2, W6, W10, W16, and W20; for PsA participants who do not meet criteria for moderate-to-severe PsO: W16 and W20), the participants or care givers will administer the provided ixekizumab prefilled syringes.

The investigator or his/her designee is responsible for the following:

- explaining the correct method of dose administration to the participant or participant's caregiver;
- explaining the correct use of the investigational agent(s) to site personnel/legal representative;
- verifying those instructions are followed properly;
- maintaining accurate records of study intervention dispensing and collection; and
- returning all unused medication to Lilly or its designee at the end of the study

During study visits, the investigator or his/her designee will administer the ixekizumab prefilled syringes to the participant. When the dosing is scheduled at home, the participants or care givers will administer the provided ixekizumab prefilled syringes.

Note: In some cases, sites may destroy clinical trial material if during the investigator site selection, the evaluator has verified and documented that the site has appropriate facilities and written procedures for disposing of clinical trial materials.

Induction Dosing Period (Period 2) (Table RHCZ.6.2)

- At Week 0, a 160-mg starting dose of ixekizumab (two 80-mg injections), followed by ixekizumab 80 mg Q2W from Weeks 2 through 12 for PsO participants with no active PsA and PsA participants who meet criteria for moderate-to-severe PsO.

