- At Week 0, a 160-mg starting dose of ixekizumab (two 80-mg injections), followed by ixekizumab 80 mg Q4W from Weeks 4 through 12 for PsA participants who do not meet the criteria for moderate-to-severe PsO participants.

Maintenance Period (Period 3) (Table RHCZ.6.2)

- Ixekizumab 80 mg Q4W (i.e., at Weeks 16 and 20).

Table RHCZ.6.2 presents the number of injections administered at each study week, for each dosing period.

Table RHCZ.6.2. Dosing Summary for the Induction and Maintenance Periods

Dosing Period	Study Week	Ixekizumab Treatment Group ^a	
		Ixekizumab (80 mg)	
		PsO Participants with no active PsA and PsA Participants Who Meet Criteria for Moderate-to-Severe PsO ^b	PsA Participants Who Do Not Meet Criteria for Moderate-to-Severe PsO ^c
Induction Dosing Period 2	0	2 ^a	2 ^a
	2	1	-
	4	1	1
	6	1	-
	8	1	1
	10	1	-
	12	1	1
Maintenance Period 3	16	1	1
	20	1	1
	24	-	-

Abbreviations: PsA = psoriatic arthritis; PsO = psoriasis; Q2W = every 2 weeks; Q4W = every 4 weeks; Q8W = every 8 weeks; SC = subcutaneous.

^a A starting dose of 160 mg (Week 0) of ixekizumab will be given as 2 SC injections at Week 0.

^b For PsO participants with no active PsA and PsA participants who meet criteria for moderate-to-severe PsO, during the Induction Dosing Period, ixekizumab (80 mg) will be given as 1 SC injection Q2W (i.e., Weeks 2, 4, 6, 8, 10, and 12). During the Maintenance Period, ixekizumab (80 mg) will be given as 1 SC injection Q4W (i.e., Weeks 16 and 20).

^c For PsA participants who do not meet criteria for moderate to severe PsO, ixekizumab (80 mg) will be given as 1 SC injection Q4W (i.e., Weeks 4, 8, 12, 16, and 20).

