IL-17, IL-23p19 antagonists, other than the 2 products used as part of this protocol.	Not permitted	Must have never received ixekizumab or IL-23p19 antagonists; or participated in any study investigating IL-23p19 antagonists. Participant with previous exposure to another IL-17 antagonist(s) will be limited to approximately 15% of the total participant population.
Natalizumab or other agents targeting α 4 integrin	Not permitted	Must have never received.
Phototherapy (including either oral and topical PUVA light therapy, UVB, or self-treatment with tanning beds or therapeutic sunbathing)	Not permitted	Must not have received within 4 weeks of baseline (Week 0, Visit 2).

Concomitant Medications Permitted/Not Permitted in the Study and Conditions for Use

Drug Class	Permitted/Not Permitted	Conditions for Use
Systemic nonbiologic psoriasis therapy (e.g., oral PUVA light therapy, cyclosporine, corticosteroids, MTX, oral retinoids, mycophenolate mofetil, thioguanine, hydroxyurea, sirolimus, azathioprine, fumaric acid derivatives, apremilast, and 1,25 dihydroxy vitamin D3 and analogues)	Not permitted (for PsO participants) Permitted (for PsO participants who met PsA criteria and PsA participants) with conditions	Must not have received within 4 weeks of baseline (Week 0, Visit 2). Stable dose allowed. Stable doses with no dose adjustments, changes, and/or introduction of a new csDMARD Allowed doses: 
 • Oral or parenteral MTX; 10 to 25 mg/week • Leflunomide: up to 20 mg/day • Sulfasalazine: up to 3 g/day • Cyclosporine: up to 5 mg/kg/day
Vaccine, Bacillus Calmette-Guérin	Not permitted	Must not have received within 12 months of baseline (Week 0, Visit 2). Should not receive within 12 months of completed treatment in this study.
Vaccines, live	Not permitted	Must not have received within 12 weeks of baseline (Week 0, Visit 2). Should not receive within 15 weeks of completed treatment in this study.
Vaccines, non-live seasonal and/or emergency	Permitted with conditions	Killed/inactive, RNA vaccine, or subunit vaccines are expected to be safe; however, their efficacy with concomitant ixekizumab treatments is unknown. Check with Lilly Medical Team (CRS/CRP) before administration.

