8.1. Efficacy Assessments

The secondary endpoints for PsO group are:

- Proportion of participants who achieve the following PASI scores: PASI 75 (defined as 75% improvement from baseline in PASI) at Week 12
- Proportion of participants with an sPGA score of 0 or 1 (0, 1) at Week 12.

The secondary endpoints for PsA group are:

- Proportion of PsA participants achieving ACR20 at Week 24.

Exploratory endpoints include, but not limited to, DAS-28-CRP and ACR individual components.

For PsO participant who also meet active PsA definition, both PsA and PsO outcomes will be collected for that participant. Likewise, to fulfill the study objective, PsO outcomes will be collected among all the PsA participants with 3% or more BSA of PsO ([Table RHCZ.8.1](#)).

Table RHCZ.8.1. Efficacy Assessments

Assessments	PsO Participants with No Active PsA	PsA Participants with	
		≥3% BSA of PsO	<3% BSA of PsO
Clinician assessments	
 • PASI • Percentage of BSA - Psoriasis • sPGA • PGA Disease Activity VAS 	
 • TJC/SJC (68/66 joints) • PGA of Disease Activity VAS -Psoriasis • PGA of Disease Activity VAS - PsA • PASI • Percentage of BSA - Psoriasis • sPGA • DAS28 - CRP^a • ACR20/50/70^a 	
 • TJC/SJC (68/66 joints) • PGA of Disease Activity VAS - PsA • DAS28 - CRP^a • ACR20/50/70^a
Patient assessments	
 • Patient's Global Assessment of disease activity VAS - Psoriasis 	
 • HAQ-DI • PsA Pain assessment question included in HAQ-DI • Patient's Global Assessment of Disease Activity VAS - PsA • Patient's Global Assessment of Disease Activity VAS - Psoriasis 	
 • HAQ-DI • PsA Pain assessment question included in HAQ-DI • Patient's Global Assessment of Disease Activity VAS - PsA

Abbreviations: ACR20/50/70 = 20%/50%/70% improvement in American College of Rheumatology response criteria; BSA = body surface area;

CRP = C-reactive protein; DAS28 = Disease Activity Score-28; HAQ-DI = Health Assessment Questionnaire – Disability Index; PASI = Psoriasis Area and Severity Index; hs-CRP = high-sensitivity C-reactive protein; PGA = Physician's Global Assessment; PsA = psoriatic arthritis; PsO = plaque psoriasis; SJC = swollen joint count; sPGA = static Physician's Global Assessment; TJC = tender joint count, V = visit; VAS = visual analog scale.

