8.3.3. Adverse Events of Special Interest

The following adverse events of special interest (AESIs) will be used to determine the safety and tolerability of ixekizumab over the range of doses selected for this clinical study.

Adverse events of special interests for ixekizumab are the following:

- cytopenias (leukopenia, neutropenia, and thrombocytopenia),
- liver function test changes/enzyme elevations (ALT, AST, bilirubin, and ALP),
- infections,
- injection-site reactions,
- allergic reactions/hypersensitivities,
- cerebro-cardiovascular events,
- malignancies,
- inflammatory bowel disease (IBD), and
- depression.

Sites will provide details on AEs as instructed on the eCRF. Investigators will also educate participants and/or caregivers about the symptoms of systemic allergic/hypersensitivity reactions and will provide instructions on the management and reporting of these reactions. Blood samples will be collected as soon as possible for any participant who experiences an AE of a potential systemic allergic/hypersensitivity reaction during the study, as judged by the investigator. These samples may be tested for antidrug antibodies (ADAs), other laboratory tests needed to elucidate the cause of the allergic/hypersensitivity reaction, and/or ixekizumab serum concentration.

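### The rubber or latex allergy exclusion [45] binds only PsO participants, although every participant is dosed from the same prefilled syringes

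*Protocol*

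**What the plan says.** Protocol Section 5.2 sets out the exclusions in three blocks: criteria for everyone ([12] to [41]), criteria for PsO participants ([42] to [45]) and criteria for PsA participants ([46] to [61]). Criterion [45], the last in the PsO block, reads "Have allergy to rubber or latex".

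Two criteria in the common block come near the subject:

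- [16] is about drug allergy: "Have a known allergy or hypersensitivity to any biologic therapy that would pose an unacceptable risk to the patient".
- [36] is a general discretionary clause: "Have any other condition that precludes the patient from following and completing the protocol, in the opinion of the investigator".

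Section 6.1 makes no distinction by indication in how the drug is given: "During study visits, the investigator or his/her designee will administer the ixekizumab prefilled syringes to the participant". Home doses also come from prefilled syringes under both regimens. For the group that matters here, footnote c of Table RHCZ.6.2 says: "For PsA participants who do not meet criteria for moderate to severe PsO, ixekizumab (80 mg) will be given as 1 SC injection Q4W".

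**The concern.** The other three criteria in the PsO block concern psoriasis treatment, psoriasis type and recent flare. Allergy to rubber or latex has no evident link to psoriasis. It would ordinarily be an exclusion because of the materials a participant is exposed to when dosed, and the dosing device is the same in both groups.

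If the allergy matters for this syringe, PsA participants without moderate-to-severe PsO are enrolled without a screen that the sponsor thought necessary for others. If it does not matter, PsO candidates are turned away for no reason. The present placement fits neither case. The stake is participant protection at entry, in a study whose purpose is safety and which lists allergic reactions and injection-site reactions as adverse events of special interest. Estimation of the endpoints is not at stake.

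**Working it through.** The Protocol gives no figure to reproduce. The check is a reading of the criteria, followed by a count of who falls outside [45].

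**1. Is the allergy named anywhere else?**

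| Block in Section 5.2 | Criteria | Number | Names rubber or latex allergy |
|---|---|---|---|
| Common | [12]–[41] | 41 − 12 + 1 = 30 | none |
| PsO participants | [42]–[45] | 45 − 42 + 1 = 4 | [45] only |
| PsA participants | [46]–[61] | 61 − 46 + 1 = 16 | none |

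The only other use of the word latex in the Protocol is in the CASPAR criteria (Section 10.6), where it describes a rheumatoid-factor test method and is unrelated.

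**2. Do the block headings really restrict?** Yes. Criterion [42] excludes PsO participants who received methotrexate within 4 weeks before baseline. Criteria [46] and [49] allow methotrexate for PsA participants at a stable dose. Both cannot apply to the same person, so the PsO block cannot be read as applying to everyone.

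**3. Who is outside [45]?** The Protocol sometimes counts patients with both conditions as PsO participants. Table RHCZ.6.3 has "Permitted (for PsO participants who met PsA criteria and PsA participants) with conditions", and Section 8.1 has "For PsO participant who also meet active PsA definition, both PsA and PsO outcomes will be collected for that participant". A PsA candidate who also has moderate-to-severe PsO may therefore already be screened against [45]. The point is confined to PsA candidates who do not meet the moderate-to-severe PsO criteria.

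**4. Are they exposed to the same device?** Yes. From Table RHCZ.6.2, this group receives 2 injections at Week 0 and 1 each at Weeks 4, 8, 12, 16 and 20: 2 + 5 = 7 injections. The Week 16 and Week 20 doses are given at home.

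**5. How large is the group?** Section 9.7 plans about 250 participants, 150 PsO and 100 PsA. The ceiling is 100/250 = 40%, reached only if no PsA participant has moderate-to-severe PsO. The Protocol does not give that split, so the shares below are assumptions.

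| Assumed share of PsA participants without moderate-to-severe PsO | Participants outside [45] | Share of 250 |
|---|---|---|
| 25% | 0.25 × 100 = 25 | 10% |
| 50% | 0.50 × 100 = 50 | 20% |
| 75% | 0.75 × 100 = 75 | 30% |

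These are people not screened against [45], not people with the allergy. The Protocol gives no prevalence, so the number with the allergy cannot be computed.

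**The case against.** The strongest reply is that no harm is shown. The Protocol does not describe the syringe's materials. That information would sit in the package insert, the Investigator's Brochure or the Pharmacy Manual. If the device contains neither material, the PsA list is right as it stands and [45] is merely surplus. On this view the matter is a query to the sponsor. The premise stands: a risk is not established. It does not rescue the text, because whichever way the query is answered, a criterion that binds one group of users of the device and not another needs editing.

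A second reply is that an investigator could still exclude an allergic PsA candidate under [36]. That is true, so such a candidate is not certain to be enrolled. But [36] is a matter of opinion and names no allergy, and naming the allergy for one group invites the inference that it is acceptable in the other. Criterion [16] does not help, since it concerns biologic therapy and not device materials.

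A third reply points to safeguards after entry:

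- Section 8.3.3 states: "Investigators will also educate participants and/or caregivers about the symptoms of systemic allergic/hypersensitivity reactions". It also provides for blood samples after suspected systemic reactions.
- Section 7.1.1 stops treatment after certain hypersensitivity reactions.
- The Schedule of Activities requires at least 1 hour of observation after the Week 0 dose.
- For the group in question, the doses at Weeks 0, 4, 8 and 12 are given at the site.

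These reduce the practical consequence, but all of them act after exposure and none screens at entry.

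Finally, the counts above measure reach and not risk. That is correct, and they should be read only in that way.

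**Conclusion.** The point holds. The sponsor's own allergy exclusion applies to PsO participants and not to PsA participants without moderate-to-severe PsO, who use the same syringes, and the Protocol gives no reason for the difference. The group not reached is at most about 100 of 250 planned participants, or 25 to 75 under the assumed shares.

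The conclusion rests on reading the block headings as restrictive, which the methotrexate rules require, and on treating patients with both conditions as possibly covered already. It does not rest on any assumption about the syringe's composition, and it claims no effect on an endpoint, an analysis or a comparison of regimens. It is a low-cost improvement that should be made.

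**What to change.** Move [45] from the PsO block to the common exclusion list, beside [16], so that it applies to every participant. If the sponsor confirms that the prefilled syringe contains neither rubber nor latex, delete [45] instead.

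Either way, one line of Section 5.2 changes. The sample size and the analyses are untouched. Moving the criterion should lose very few eligible PsA patients, although the Protocol gives no prevalence with which to put a number on that loss.
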